10.3.6 Safety Follow-Up Assessment

Patients will return to the clinic or will be contacted for a safety follow-up assessment 30 days \pm 3 days after the last dose of study drug was taken; or earlier if subsequent therapy for advanced malignancy is initiated prior to 30 days \pm 3 days. Only information about AEs and SAEs will be collected at this visit.

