10.4.4 Time Period and Frequency for Event Assessment and Follow-up

The occurrence of an AE or SAE may come to the attention of study personnel during study visits and interviews of a study patient presenting for medical care, or upon review by a study monitor. At each study visit, the investigator or their designee will inquire about the occurrence of AE/SAEs since the last visit.

Any medical condition that is present at the time that the patient is screened will be considered as baseline and not reported as an AE. However, if the study patient's condition deteriorates at any time during the study, it will be recorded as an AE.

Changes in the severity of an AE will be documented to allow an assessment of the duration of the event at each level of severity to be performed. AEs characterized as intermittent require documentation of onset and duration of each episode.

All reportable events will be recorded with start dates occurring any time after informed consent is obtained through and including 30 calendar days after the last administration of ulixertinib. Any SAE occurring after the reporting period must be promptly reported if a causal relationship to the study product is suspected. If the patient begins a new anti-cancer therapy, the safety reporting period ends at the time the new treatment is started, however, death must always be reported when it occurs during the 30-day reporting period irrespective of intervening treatment.

All events will be followed for outcome information in accordance with good medical practice until they are resolved, stabilize, or judged no longer clinically significant or, if a chronic condition, until fully characterized. Any AEs that are considered drug-related (possibly related, related) must be followed until resolution or until stabilization.

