11.5.7.1 Adverse Events (AE)

AEs will be coded using the Medical Dictionary for Regulatory Activities (MedDRA). System Organ Class, High-Level Group Term, High Level Term, Preferred Term, and Lower-Level Term will be attached to the clinical database.

AEs will be summarized based on the date of onset for the event. Summaries (number and percentage of patients) of treatment-emergent AEs will be provided by System Organ Class and Preferred Term, by group/tumor histology and overall.

Treatment-emergent adverse event (TEAE) is defined as any AE that emerges during treatment having been absent pre-treatment or worsens relative to the pre-treatment state.

Events that are considered study drug-related, deaths, SAEs, and AEs resulting in study drug discontinuation will also be tabulated by System Organ Class and Preferred Term.

A tabulation will also be provided that summarizes treatment-emergent AEs by maximum severity (i.e., CTCAE grade).

All AEs, including treatment-emergent and non-treatment-emergent AEs, will be listed in patient data listings.

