**Table 2. Analysis periods**

Phase	Period	Definition
Part A and Part B	PRE-TREATMENT	From informed consent form (ICF) signature to the day before first dose of study treatment.
	ON-TREATMENT	From the day of first dose of study treatment to ≤14 ± 3 days after last dose of study treatment (date of EOT visit), or the earliest date of subsequent anti-cancer drug therapy – 1 day, whichever occurs first.
	FOLLOW-UP	From day ≤14 ± 3 after last dose of study treatment, or the earliest date of subsequent anti-cancer drug therapy, whichever occurs first, to end of study. End of study is date of completion / discontinuation from the study as collected in the CRF or the last recorded assessment in the database if the patient has not completed/discontinued the study at the time of the analysis.

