### 9.9.1 Adverse Events (AEs)

The following definitions will be used:

- **Treatment-emergent AEs (TEAEs):** Treatment-emergent adverse event (TEAE) is defined as any AE that emerges during on-treatment period, after the 1st dose of the study agent.
- **Related AEs:** AEs suspected by the Investigator and/or Sponsor to have a relationship to study treatment (as recorded on the AE eCRF page, Causality = Related, Possibly Related, or missing).
- **Serious Adverse Events (SAE):** serious AEs (as recorded on the AE eCRF page, Does AE Meet the Definition of an SAE = Yes).
- **AEs leading to treatment discontinuation:** AEs leading to permanent discontinuation of study treatment (as recorded on the AE eCRF page, Action taken with study treatment = Drug withdrawn).
- **AEs leading to dose reduction:** AEs leading to dose reduction of study treatment (as recorded on the AE eCRF page, Action taken with study treatment = Dose Reduced).
- **AEs leading to treatment interruption:** AEs leading to treatment interruption of study treatment (as recorded on the AE eCRF page, Action taken with study treatment = Drug Interrupted).
- **AEs leading to Death:** adverse event leading to death (as recorded on the AE eCRF page, Results in death, or Outcome = Fatal, or Grade = 5).

An overview summary table will present the number and percentage of patients with a TEAE, including:

- TEAEs / TEAEs related to study treatment

- SAEs / SAEs related to study treatment
- TEAEs leading to treatment discontinuation / TEAEs related to study treatment leading to treatment discontinuation
- TEAEs leading to treatment discontinuation within 1 cycle / TEAEs related to study treatment leading to treatment discontinuation within 1 cycle
- TEAEs leading to treatment discontinuation following 1 cycle / TEAEs related to study treatment leading to treatment discontinuation following 1 cycle
- TEAEs leading to treatment interruption / TEAEs related to study treatment leading to treatment interruption
- TEAEs leading to treatment interruption within 1 cycle / TEAEs related to study treatment leading to treatment interruption within 1 cycle
- TEAEs leading to treatment interruption following 1 cycle / TEAEs related to study treatment leading to treatment interruption following 1 cycle
- TEAEs leading to dose reduction / TEAEs related to study treatment leading to dose reduction

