- TEAEs leading to dose reduction within 1 cycle / TEAEs related to study treatment leading to dose reduction within cycle 1
- TEAEs leading to dose reduction following 1 cycle / TEAEs related to study treatment leading to dose reduction following cycle 1
- TEAEs leading to death / TEAEs related to study treatment leading to death
- TEAEs with grade  $\geq 3$  / TEAEs related to study treatment with grade  $\geq 3$

In addition, the following tables will be produced by SOC and PT:

- TEAEs / TEAEs related to study treatment
- Serious TEAEs / Serious TEAEs related to study treatment
- TEAEs and maximum CTCAE grade / TEAEs related to study treatment and maximum CTCAE grade
- TEAEs leading to treatment within/following discontinuation / TEAEs related to study treatment leading to treatment discontinuation
- TEAEs leading to treatment within/following interruption / TEAEs related to study treatment leading to treatment interruption
- TEAEs leading to dose reduction within/following cycle 1 / TEAEs related to study treatment leading to dose reduction within/following cycle 1
- TEAEs leading to death / TEAEs related to study treatment leading to death

The following tables will be produced by PT:

- TEAEs / TEAEs related to study treatment
- Serious TEAEs / Serious TEAEs related to study treatment

A patient with multiple occurrences of an AE will be counted only once in the AE category. SOCs will be sorted by descending order of frequency for the overall group, PTs will be sorted by descending order of frequency for the overall group within each SOC.

All deaths will be summarized and listed with the corresponding reasons, split by overall deaths, and deaths occurring after the first dose of ulixertinib.

The following listings will be provided:

- All AEs
- TEAEs
- SAEs
- Deaths

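### The SAP closes the TEAE window at the End of Treatment visit, so adverse events collected from then to day 30 after last dose stay out of up to 9 of the 27 final TEAE tables

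*SAP*

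**What the plan says.** SAP 9.9.1 defines a TEAE as "any AE that emerges during on-treatment period", after the first dose. SAP Table 2 ends the on-treatment period by the phrase "to ≤14 ± 3 days after last dose of study treatment (date of EOT visit"), or on the day before subsequent anti-cancer drug therapy if that comes first. The SOC/PT tables in SAP 9.9.1 are then built on TEAEs, for example "Serious TEAEs / Serious TEAEs related to study treatment".

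The protocol collects for longer. Section 10.4.4 records events with onset "through and including 30 calendar days after the last administration of ulixertinib". Collection closes early if new anti-cancer therapy starts, but "death must always be reported when it occurs during the 30-day reporting period irrespective of intervening treatment". Section 10.3.6 adds a contact at day 30 ± 3 and says of it: "Only information about AEs and SAEs will be collected at this visit".

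Protocol 11.5.7.1 defines a TEAE as an event arising during treatment, either "having been absent pre-treatment or worsens relative to the pre-treatment state". It gives no end day. It also says: "Events that are considered study drug-related, deaths, SAEs, and AEs resulting in study drug discontinuation will also be tabulated". It closes by sending all events, treatment-emergent or not, to the listings.

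SAP 7.2 says that the study stopped early and that the final report will be abbreviated and focused on safety. SAP Section 11 mentions the added analysis population and the reduced demographic reporting. It does not mention the TEAE definition.

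**The concern.** The sponsor pays for a safety contact whose only purpose is to capture adverse events up to day 30, and then uses an analysis window that ends about two weeks earlier. In a report focused on safety, the summary tables are what most readers will use. Events with onset after EOT are absent from them even if they are severe or judged related to the drug. Because the window ends at each patient's own EOT visit, its length also differs between patients for reasons unrelated to drug exposure.

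Two smaller defects go with this. The end date is not defined for every patient. The SAP also drops the protocol's limb on worsening from the pre-treatment state without recording the change.

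**Working it through.** The plan gives no figure to reproduce. The check is a count of tables, day arithmetic, and a comparison of shells.

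**Tables affected** (SAP list of tables, column for inclusion in the final analysis)
- Tables 14.3-1.1 to 14.3-1.31 concern TEAEs: 31. Table 14.3-1.32 summarises deaths and is not a TEAE table.
- Not flagged for the final analysis: 14.3-1.6 to 14.3-1.9, so 31 − 4 = 27.
- Tables 14.3-1.12 to 14.3-1.29 (18) require discontinuation, interruption or dose reduction. An event that starts after EOT cannot cause these, since drug has already stopped. 27 − 18 = 9.
- The nine are 14.3-1.1, 1.2, 1.3, 1.4, 1.5, 1.10, 1.11, 1.30 and 1.31.

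Nine is a ceiling. An event would have to be serious, related and fatal to bear on all of them. In addition, the Any SAE rows of Table 14.3-1.1 and the programming note for Table 14.3-1.5 refer to SAEs without repeating the TEAE limit, so late SAEs could be let in there.

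**Days left out**

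Days left out = 30 − EOT day, with no new therapy by day 30.

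| EOT day after last dose | Days left out | Share of the 30 days |
|---|---|---|
| 17 | 30 − 17 = 13 | 13/30 = 43% |
| 14 | 30 − 14 = 16 | 16/30 = 53% |
| 11 | 30 − 11 = 19 | 19/30 = 63% |

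The visit is planned for at most 14 ± 3 days, so an earlier EOT is allowed and widens the gap. The last column is a share of calendar days, not of adverse events.

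New therapy narrows the gap. If it starts on day 21 (my assumption), collection ends on day 20, and 20 − 17 = 3 or 20 − 14 = 6 days are left out. If it starts before EOT, the gap is 0, apart from deaths up to day 30.

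**Where the end date fails**
- No EOT visit: Table 2 yields no date. SAP 7.5 completes partial dates only, and no other rule fills the gap.
- Late EOT visit: protocol 8.1.3 takes a patient off treatment after a dose delay of more than 21 days, so EOT falls on about day 22 at the earliest. Protocol 10.3.5 and Table 2 expect it by day 17. If the actual visit date governs, at most 30 − 22 = 8 days are left out. If the 17-day limit governs, 13 are.

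**Where late events remain visible**
- Listing 16.2.7-1 (all events, flagged for the final analysis) keeps them. Its shell has no grade or causality column, although a footnote cites CTCAE.
- Listing 16.2.7-2 has both columns but holds TEAEs only.
- Listing 16.2.7-3 repeats 16.2.7-2 for serious events. Whether it keeps late SAEs can be read either way.
- Table 14.3-1.32 and Listing 16.2.7-4 keep deaths. That listing calls any death after ulixertinib treatment-emergent, with no end date, so a late death can carry the flag while its causal event is missing from Table 14.3-1.30.

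**Worsening.** Under protocol 10.4.4, deterioration of a condition present at screening is recorded as an adverse event anyway. The dropped wording therefore matters mainly for events that start between consent and first dose and then worsen.

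**The case against.** The strongest reply is that the SAP breaks no rule. The protocol defines a TEAE as arising during treatment, and the SAP window already runs past the last dose. Protocol 11.5.7.1 itself sends non-treatment-emergent events to listings, and Listing 16.2.7-1 does that. This stands: a reader might infer that the SAP contradicts the protocol, and the documents do not support that.

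A reader might also infer that the protocol requires related events, deaths and SAEs to be tabulated without a TEAE limit, so that the SAP has silently restricted them. The sentence can be read so. But it follows the TEAE definition and precedes the TEAE severity table, and reading its events as TEAEs is at least as natural. I do not rest the point on it.

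Nor is it right that the window has no workable end. A dated EOT visit gives one; the defect is confined to missing or late visits. SAP 7.5 concerns missing data and would not bar a rule for deriving the period.

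The death flag is largely a labelling matter, since SAP 9.9.1 already separates all deaths from those after first dose.

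What survives is that data collected specifically for safety are kept out of the safety summaries, and that for late non-serious events the grade and causality may appear in no final output.

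**Conclusion.** The point holds as a cheap improvement to a stated rule. With no new anti-cancer therapy and EOT in window, at least 13 of the 30 collected post-dose days lie outside the TEAE window, and more if EOT is earlier than day 17. Up to 9 of 27 final TEAE tables are affected. The end date is undefined when EOT is missing and ambiguous when it falls after day 17.

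How many events this removes cannot be worked out from the documents. It would be tempting to read 43% or 53% as the share of post-dose events lost, or as its upper limit. Neither is supported: these are fractions of calendar days at two EOT dates, an earlier EOT gives more, and the documents give no onset rate after last dose. The half-life of 2–4 hours reported across animal species does not supply one.

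Part A is single-arm and descriptive, so no treatment comparison is biased. The consequence is incomplete summary counts over a window that varies between patients.

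**What to change.** In SAP 9.9.1, define the TEAE window apart from the on-treatment period: onset, or worsening from the pre-treatment state, from first dose through 30 days after last dose, or until new anti-cancer therapy if earlier, with deaths kept to day 30 as in protocol 10.4.4. Keep the on-treatment period for laboratory data, vital signs and concomitant medications.

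In SAP Table 2, state which date governs when the EOT visit is missing or late. Protocol 8.1.3, protocol 10.3.5 and Table 2 must be reconciled.

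Apply the same window to the SAE rows of Table 14.3-1.1, Table 14.3-1.5, Listing 16.2.7-3 and the death flag in Listing 16.2.7-4. Add grade and causality to Listing 16.2.7-1. List the changed TEAE definition in Section 11.

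The cost is one definition, one sentence, one dataset flag, a few shell edits and a Section 11 entry. The data are already collected. The downside is that TEAE counts rise slightly and may include some unrelated events. Because protocol 10.4.2 has fatal progression reported as a Grade 5 event, Table 14.3-1.30 would gain some disease-progression deaths. Patients who start new therapy would still have a shorter window.

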### 7.4 SOFTWARE

The SAS Viya version 3.5 (or higher), will be used for all analysis, unless otherwise specified.

### 7.5 MISSING DATA HANDLING

No imputation for missing data will be carried out other than to complete partial dates using standard imputation techniques as described below in [Section 7.6](#).

## 7.6 PARTIAL DATE IMPUTATION

Detailed rules for partial date imputation are described below.

A permanent new date variable should be created if there is a requirement to be used in determining flags (such as on-treatment flags), sort orders and other derived variables needed for a table, listing, or figure. Imputed date variable names will be defined in the derived dataset specifications.

Original (raw) date variables must not be overwritten. Imputed dates will not be displayed in the listings.

### **General rules for Adverse events (AE) and prior and concomitant medications (CM)**

#### *In case of partial dates with missing day:*

For AE and CM, any partial start date during the month of first dosing will be imputed to be the date of first dose, taking the worst-case scenario.

For any AE and CM starting after the month of first dosing, the start date will be imputed to be the first day of the month.

For any AE and CM starting before the month of first dosing, the start date will be imputed to be the last day of the month.

Partial AE and CM end dates will be imputed to be the last day of the month or at the date of study discontinuation/completion, whichever occurs first.

#### *In case of partial dates with missing day and missing month:*

For AE and CM, any partial start date during the year of first dosing will be imputed to be the date of first dose, taking the worst-case scenario.

For any AE and CM starting after the year of first dosing, the start date will be imputed to be the first day of the year (i.e. 01 January).

For any AE and CM started before the year of first dosing, the start date will be imputed to be the last day of the year (i.e. 31 December).

Partial AE and CM end dates will be imputed to be the last day of year (i.e. 31 December) or at the date of study discontinuation/completion, whichever occurs first.

Some examples are given below (DDMMYY).

In most cases, start dates are imputed as first day of the month or first of January.

**Table 3: Examples of missing dates imputation**

Data Type	Start Date	Imputed Start Date	First Dose date	End Date	Imputed End Date
Adverse Event, Prior/Concomitant Meds	JAN2017	31JAN2017	11NOV2017	MAR2017	31MAR2017
Adverse Event, Prior/Concomitant Meds	MAR2017	01MAR2017	27JAN2017	MAR2017	31MAR2017
Adverse Event, Prior/Concomitant Meds	2017	27JAN2017	27JAN2017	2017	16MAR2017 E
Adverse Event, Prior/Concomitant Meds	MAR2017	01MAR2017	27JAN2017	MAR2017	01MAR2017*
Adverse Event, Prior/Concomitant Meds	JAN2017	31JAN2017	27FEB2017	2017	31DEC2017

E Patient discontinued on 16MAR2017; \* Patient discontinued on 01MAR2017.

### Rules for other partial dates

Partial dates are not expected for death. However, should a partial date be present for death, the date will be imputed to be the day after the last visit/assessment date when the patient was known to be alive, if there is at least one visit/assessment during the month of the corresponding partial death date. If there is no visit/assessment performed during the month of the corresponding partial death date, then the partial death date would be imputed as the first day of the month. A similar approach will be followed for partial date for death in which only year is known.

If partial date is present for dates related to disease history, the same rules as for AE and CM will be applied.

### 7.7 VISIT WINDOWING

Planned assessments will not be re-assigned to any planned visits using statistical programming based on assessment date. All the data will be analysed according to the planned visit as collected in the eCRF. Data obtained at unscheduled and repeat assessments will be considered for the derivation of baseline, worst on-treatment result for safety analyses (clinical safety laboratory evaluation, other safety data), and time to event analyses.

## 7.8 REPORTING GUIDELINES

### Visit labels

The visit labels displayed in [Table 4](#) will be used to display results in the TFLs. Following Cycle 2, any subsequent Cycle will consider Day 1 as start of Cycle and not the days since first study dose as for Cycle 2.

**Table 4. Visit Labels**

Period	Visit	TFLs Label
Part A and Part B		
Screening: Day -28 to Day -1	Screening Day -28 to Day -1	Screening
Cycle 1	Cycle 1 Day 1	Baseline
	Cycle 1 Day 8	C1D8
	Cycle 1 Day 15	C1D15
Cycle 2	Cycle 2 Day 29	C2D29
	Cycle 2 Day 36	C2D36
	Cycle 2 Day 43	C2D43
Cycle 3	Cycle 3 Day 1	C3D1
...	...	...
Cycle n	Cycle n Day 1	CnD1
End of Treatment: $\leq 14 \pm 3$ days after last dose of study treatment.	End of Treatment Visit	EOT
Safety Follow-Up: $30 \pm 3$ days after last dose of study treatment.	Safety Follow-Up	SFU
Follow-Up: every three months ( $\pm 7$ days) until death, end of the study, or patient withdrawal of consent, whichever comes first.	Follow-Up	FUn

### Summaries of baseline and change from baseline

Baseline and change from baseline will be calculated for all assessments, including additional assessments (if applicable), as follows:

- Baseline is defined as the last available assessment prior to first dose of study treatment, including additional assessments (where applicable). Assessments that occurred on the same day as first dose, when time of assessment is not available, will be assumed to be prior to first dose (unless the assessment is planned after first dose in the protocol).
- Change from baseline will be calculated as the difference between the post-baseline assessment value and the baseline value.

Whenever applicable, percent change from baseline will be calculated as the difference between the post-baseline assessment value and baseline value divided by the baseline value multiplied by 100.

### **Unscheduled visit / Repeat assessments**

Data obtained at unscheduled and repeat assessments will be considered for the derivation of baseline, worst on-treatment result for safety analyses (clinical safety laboratory evaluation, other safety data), and time to event analyses.

All other data from unscheduled or repeat assessments will not be included in summaries and will only be presented in data listings, if not otherwise specified.

### **N**

N will be the number of patients in the specified population and group.

### **Summary presentation**

For Part A all outputs will be presented by molecular alteration group as defined in SAP section 6.1 and overall if not otherwise specified. For Part B, all outputs will be presented by the selected histology groups, physicians choice of treatment (pooling all treatments under just one group) and overall.

